10.2.17. ECOG Performance Status

ECOG performance will be summarized categorically with a shift from baseline to the worst post-baseline by cycle and for all cycles. Individual subject data will be listed. The ECOG performance score collected as Cycle 1 Day 1 will be used as the baseline value.

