- e. Red blood cell transfusion history must be available for the 56 days immediately preceding and including the date of randomization and platelet transfusion history must be available for the 56 days immediately preceding and including the date of randomization. Transfusion history data can be gathered during the 56-day screening period as detailed in [Section 6.1.2](#).
- f. Thrombocytopenia at baseline must be confirmed by two platelet counts that are $\leq 75 \times 10^9/L$ and ≥ 21 days apart. The second confirmatory platelet count must be obtained ≤ 14 days prior to randomization. At least one platelet count must be centrally analyzed within the 56 day screening period with results of $\leq 75 \times 10^9/L$; the second platelet count may be centrally or locally analyzed, with results that are also $\leq 75 \times 10^9/L$. If additional platelet counts are obtained during the interim period, these must also have been $\leq 75 \times 10^9/L$. If platelet counts within the interim period are $> 75 \times 10^9/L$, this would be acceptable only if associated with a platelet transfusion administered within 7 days prior to the date of the platelet count ([Section 6.1.3](#)).
- g. Prior Treatment for MDS includes all prior treatments for MDS regardless of discontinuation date of treatment as detailed in [Section 6.1.5](#).
- h. All medications taken in the 8 weeks (56 days) prior to randomization are to be collected on the appropriate Case Report Form (CRF).
- i. The assessment does not need to be performed if the screening examination was performed within 7 days of the first dose of IP in the treatment phase.
- j. Electrocardiogram will be performed locally at screening and whenever clinically indicated. The investigator will review and assess the results as detailed in [Section 6.1.9](#).
- k. Urinalysis is conducted at the central laboratory at screening and whenever clinically indicated as detailed in [Section 6.1.10](#).
- l. Coagulation is conducted at the central laboratory at screening and whenever clinically indicated as detailed in [Section 6.1.11](#).
- m. A direct or indirect Coombs' test at screening is performed at the local laboratory.
- n. The screening reticulocyte count is performed at the local laboratory.

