6.4 Baseline

Refer to [Section 10.4](#) for baseline definitions of vital signs, weight and laboratory assessments, unless noted otherwise for a particular assessment.

Physical examination, ECOG performance status, hematology or serum chemistry does not need to be performed if the screening examination was performed within 7 days of the first dose of IP in the treatment phase. Assessment of bleeding events, and the FACT-An and EQ-5D questionnaires start on Day 1 of Cycle 1. The FACT-An and EQ-5D questionnaires should always be completed prior to IP administration and, when feasible, prior to interaction with study personnel.

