6.6.9 Eastern Cooperative Oncology Group Performance Status

Eastern Cooperative Oncology Group Performance status is to be assessed before IP administration on Day 1 of each cycle in the treatment phase and at Treatment Discontinuation.

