8. DEMOGRAPHICS AND BASELINE CHARACTERISTICS

Summaries for the demographics and baseline clinical characteristics will be summarized by treatment group for ITT, mITT and the Safety population. Baseline clinical characteristics are defined as the latest data collected on or before date of randomization, if not otherwise specified. When there are retested values, the retest values will be used for the analysis. Individual subject listings will be provided to support the tables.

Summary statistics (mean, standard deviation, median, minimum, and maximum) will be provided for variables measured on a continuous scale. The frequency distribution (n, %) will be provided for those categorical variables measured on a nominal scale.

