11.3. Clinical Laboratory Evaluations

Clinical laboratory values will be presented using the reported units. Change in clinical laboratory results from baseline (last non-missing value on or prior to the date of first dose of the study drug) to each scheduled time point will be provided for the safety population. Clinical laboratory values will be graded according to CTCAE version 4.0 for applicable tests. Shift tables for change in maximum CTCAE grades of high and low lab values, separately, will be provided for the safety population by treatment for those labs that have CTCAE grades. Separate shifts tables will be provided for lowest value by cycle and highest value by cycle. Clinically significant laboratory abnormalities that meet Grade of 3 or Grade 4 criteria according to the CTCAE will be listed and summarized (counts and percentages) by cycle. Laboratory data collected after the date of the end of treatment visit, last dose date + 28 days, whichever the latest, will not be used for summary. Nadirs, the minimum values, of selected hematology parameters, ie. Hgb, platelets, absolute neutrophil count (ANC), white blood cell counts, and RBC, across all cycles and within each cycle will be summarized. The day of nadir will be summarized categorically by frequency of the day of the cycle that the nadir observation occurs, by cycle and treatment. The categories for the days within a cycle are day 1-7, Day 8-14, Day 15-21 and Day >21. The average onset day of nadir across all cycles, the analyte value at nadir by cycle, and the change from baseline to analyte value at nadir will be summarized descriptively by treatment for each selected hematology test.

A separate listing, including only values outside the normal range, if any, will also be provided. A listing of all clinical laboratory values will be provided. Separate listings will be provided for the hematology, blood chemistry, coagulation, urinalysis, erythropoietin, ferritin and serum transferrin saturation laboratory values.

Graphical display of select laboratory parameters over the course of the study will be provided (if needed).

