11.4. Vital Sign Measurements

Vital sign measurements (weight, systolic and diastolic blood pressure, pulse rate, respiration rate and temperature) as well as change from baseline will be summarized descriptively by scheduled time point. The last vital sign measurement on or prior to the date of first dose of study drug will be used as the baseline value. Frequency summaries (shift tables) of shifts from baseline to post-baseline by cycle and to the worst post-baseline value in terms of normal/abnormal will be provided for pulse, respiratory and blood pressure. The normal ranges are defined as: 60-100 beats/minute for pulse, 12 to 16 breaths/minutes for respiratory rate, 90-140 mmHg for systolic blood pressure, and 60-90 mmHg for diastolic blood pressure). Vital sign data collected after the date of the end of treatment visit, last dose date + 28 days, whichever the latest, will not be used for summary. A listing of all vital signs will be provided.

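### The ECOG shift table accepts only a Cycle 1 Day 1 baseline, an assessment the protocol lets sites skip after recent screening, and the SAP gives no fallback

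*SAP*

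**What the plan says.** SAP 10.2.17 describes the table: "ECOG performance will be summarized categorically with a shift from baseline to the worst post-baseline by cycle and for all cycles". It then fixes the starting point: "The ECOG performance score collected as Cycle 1 Day 1 will be used as the baseline value". Nothing in that section covers a subject without such a score.

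In protocol Table 1, the ECOG cell for Day 1 of Cycles 1 and 2 carries footnote i: "The assessment does not need to be performed if the screening examination was performed within 7 days of the first dose of IP". Protocol 6.4 repeats the waiver and names ECOG: "Physical examination, ECOG performance status, hematology or serum chemistry does not need to be performed if the screening examination was performed within 7 days". Protocol 6.6.9 says that ECOG "is to be assessed before IP administration on Day 1 of each cycle in the treatment phase" and does not mention the waiver.

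SAP 8 has a general baseline rule: "Baseline clinical characteristics are defined as the latest data collected on or before date of randomization, if not otherwise specified". For on-treatment change, SAP 11.3 takes the laboratory baseline as the "last non-missing value on or prior to the date of first dose of the study drug". SAP 11.4 says of vital signs: "The last vital sign measurement on or prior to the date of first dose of study drug will be used as the baseline value". SAP 11.5 treats marrow and blood-smear values in the same way.

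**The concern.** The table depends on a single visit, and the protocol makes the assessment at that visit optional for subjects screened shortly before dosing. A site can follow the protocol exactly and still leave the analysis without the one value it accepts.

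The subjects at risk are those with the freshest screening scores. They would leave the table because of visit timing, not because information is lacking. At stake is the completeness of a descriptive summary: the shift counts would rest on fewer subjects than the data could support, and the reason would not be visible from the table. Protocol 10.7 plans ECOG change from baseline by treatment group, so the summary is a promised output.

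**Working it through.** The plan gives no figure to reproduce and no arithmetic applies, so the check compares the rules in order.

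1. **Which value is accepted?** SAP 10.2.17 accepts the Cycle 1 Day 1 score. No alternative is named.

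2. **Must that value exist?** No. Protocol 6.4 and Table 1 footnote i waive it when the screening examination was within 7 days of first dose.

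3. **Does another rule supply a substitute?**
   - SAP 8 would accept a screening score, but it applies only where nothing else is specified, and 10.2.17 does specify something else.
   - Protocol 10.4 sets a baseline for laboratory and vital-sign measures and does not name ECOG.
   - SAP 16, which lists departures from the protocol's statistical section, does not mention the ECOG baseline.

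4. **How do the neighbouring rules behave?**

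| Measure | Cycle 1 Day 1 waiver in Table 1? | SAP baseline for on-treatment change | Can a screening value serve? |
|---|---|---|---|
| Hematology, serum chemistry | Yes (footnote i) | Last non-missing up to first-dose date (11.3) | Yes |
| Vital signs | No | Last measurement up to first-dose date (11.4) | Yes |
| Marrow and blood smear | Not scheduled at Cycle 1 Day 1 | Last observed up to first-dose date (11.5) | Yes |
| ECOG | Yes (footnote i) | Cycle 1 Day 1 score (10.2.17) | Not as written |

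Hematology and serum chemistry are the closest comparison: same waiver, but a baseline rule that absorbs it.

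5. **Who is affected?** A subject loses the baseline only if all of these hold: the subject was treated; the screening ECOG fell within 7 days of first dose; the site did not repeat it; and no score was entered under the Cycle 1 Day 1 visit.

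6. **How many?** The documents give neither the gap between screening ECOG and first dose nor the use made of the waiver. The range runs from 0 to all treated subjects, hence at most 216. One indication points towards a low number: protocol 6.1.1 asks for screening marrow and hematology samples at least 14 days before randomization, and first dose does not precede randomization. A screening ECOG done alongside those samples would fall outside the 7-day window. The documents do not say that ECOG was done on that day.

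7. **What else uses this baseline?** The ECOG stratification variable for the primary and overall survival tests is derived from CRF pages (SAP 10.1 and 10.2.1), with SAP 10.1 pointing to Section 8.2. The rule in 10.2.17 does not enter those tests.

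**The case against.** The strongest reply is that the loss is only conditional. The waiver permits skipping and does not require it, and protocol 6.6.9 asks for ECOG on Day 1 of every cycle. The SAP also speaks of the score collected as, not on, Cycle 1 Day 1, which could cover a screening score recorded under that visit label. These points stand as limits on size. They do not close the gap, because no section states such a carry-forward.

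It is also fair that the consequence is small. ECOG change is not a listed endpoint, the table is descriptive, and SAP 10.2.17 provides for individual listings, so the scores remain visible. The waiver is used before the first dose in a blinded trial, so nothing in the documents suggests that missing baselines would differ by arm.

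A reader might infer two further defects that the documents do not support.

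- **Untreated subjects also drop out for want of a baseline.** SAP 5.1.3 builds cycles from non-zero dosing records. Protocol 6.6.9 schedules on-study ECOG on Day 1 of each cycle and at treatment discontinuation, and protocol 6.13 asks for discontinuation procedures in subjects who took at least one dose. An untreated subject has no scheduled post-baseline score to shift to, whatever the baseline rule.
- **Two ECOG baselines in one report are an error.** SAP 8 uses randomization for the characteristics table and yields where a section sets its own rule. The laboratory and vital-sign sections also use a first-dose anchor for on-treatment change. That pattern is the SAP's own, and the fix below would not remove the difference, since first dose may follow randomization by up to 3 days.

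**Conclusion.** The point holds as a minor one. As written, SAP 10.2.17 gives no baseline to a treated subject whose Cycle 1 Day 1 ECOG was properly skipped under the protocol's waiver, although a recent screening score exists. The number affected is unknown, may be zero, and is bounded by the treated subjects.

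This rests on reading the rule literally, without an unstated carry-forward of the screening score, and on the waiver having been used at least once. A reader should not infer that the confirmatory results are at risk: neither the primary test nor the overall survival test uses this baseline.

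**What to change.** In SAP 10.2.17, define the ECOG baseline as the last non-missing score up to and including the date of first dose. This keeps every Cycle 1 Day 1 score taken before dosing, as protocol 6.6.9 requires, fills the waived ones from screening, and matches SAP 11.3 to 11.5. A score recorded under Cycle 1 Day 1 but dated after the first dose would no longer count as baseline.

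If the existing wording was meant to include a screening score standing in for the visit, saying so would serve equally well.

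The cost is one sentence and a small programming change, with no new data. The SAP was signed in March 2019, and the rationale for Protocol Amendment 6.0 describes the primary analysis report as final as of 04-Feb-2020. For that report the change would be post hoc. The practical route is a clarification for later reporting, or a table note giving the number of treated subjects without a Cycle 1 Day 1 ECOG score, by arm. If that number is zero, nothing further is needed.

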10.3. Subgroup Analysis

In addition to analyses that include all ITT subjects, additional exploratory subgroup analyses will be performed where an adequate number of subjects are available in each subgroup to allow for meaningful interpretation of results. Analyses will be performed within the following subgroups for the RBC transfusion independence for at least 56 days and OS endpoints:

- Age group (< 65, ≥ 65 years)
- Sex (Male, Female)
- Race (White, Asian, Others)
- WHO MDS diagnosis classification (RCMD, RAEB-1, Others)
- Baseline bone marrow blasts (< 5%, ≥ 5%)

- Geographic region (North America, Europe, ROW)
- Average baseline RBC transfusion requirements prior to randomization (≤ 4 units of RBC per 28 days, > 4 units of RBC per 28 days)
- Baseline platelet transfusion status (Dependent, Independent)
- ECOG performance status (0 or 1, 2)
- Baseline Platelet Count ($\leq 50 \times 10^9/L$, $>50 \times 10^9/L - \leq 75 \times 10^9/L$)
- Prior lenalidomide use (Yes, No)
- Subject enrolled under Amendment 2 (Yes, No)
- IPSS-R risk category (Very low or low, Intermediate, High or very high)

RBC transfusion independence for 56 days and OS will be analyzed separately within each subgroup using the appropriate analysis methods as described in Section 10.1 and Section 10.2.1. The odds ratios (ORs) for RBC transfusion independence and the hazard ratios (HRs) for OS will be presented graphically in forest plots.

The OS will also be explored by whether a subject achieves RBC transfusion independence for at least 56 days or not. Kaplan-Meier estimates for median OS as well as the 25th and 75th percentiles and associated two-sided 95% CIs will be summarized for each subgroup group (Responders and Non-responders), unadjusted for the stratification variables. This will be explored for all subjects in ITT population as well as for subjects within oral azacitidine arm and within Placebo arm.

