- a. The study visit window for visit related assessments in the double-blind treatment phase is ± 3 days for Cycles 1 and 2; ± 7 days for Cycle 3 and beyond, unless noted otherwise for a particular assessment. **However, please note that in all circumstances a drug holiday of 7 days needs to be maintained for the treatment schedules of 300 mg and 200 mg for 21 days /28-day-cycle (14 and 21 days, respectively, for modified treatment schedules of 200 mg for 14 days/28-day-cycle and 7 days/28-day-cycle.** Study visits should also take into account the subject's IP supply. Only 1 cycle of IP will be dispensed to the subject on Day 1 of each cycle. Day 1 of Cycles 2 and beyond may be delayed from Day 28 of the prior cycle in order for subjects to recover from toxicity and meet criteria for re-treatment ([Section 8.2.5](#)). During follow-up, the study visit window is ± 7 days for visits scheduled monthly (including the follow-up visit 28 days after last dose if necessary) or ± 14 days for visits scheduled every 3 month. One cycle (one month) is considered as 28 days (ie, 4 weeks).
- b. First dose of IP in Cycle 1 should be administered within 3 days of randomization and can be on the same day of randomization.
- c. All subjects who have received at least one dose of IP should undergo Treatment Discontinuation procedures detailed in [Section 6.13](#) when treatment is discontinued. The reason for discontinuation will be recorded in the CRF and in the source document for all randomized subjects, regardless of whether they are dosed or not. Reasons for discontinuation are provided in [Section 12](#).
- d. MDS diagnosis, WHO classification ([Appendix A](#)), and IPSS risk classification ([Appendix B](#)) will be prospectively determined by independent central pathology and cytogenetics review, and applicable central laboratory results. Thus bone marrow aspirate and biopsy samples together with peripheral blood samples must be collected at screening as detailed in [Section 6.1.1](#). At all later time points a biopsy is only needed if adequate aspirate is not attainable. Blood samples at screening should be collected on the same day as the bone marrow aspirate/biopsy procedure. Instructions for submission of bone marrow slides, sample collection, processing, storage, and shipment procedures are provided in the study's Central Laboratory Manual.

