4.4. Sample Size

The basis for the power and sample size determination will be a test of the equality of the overall survival curves between the oral azacitidine and placebo treatment groups using a stratified log-rank test. Assuming a median OS of 18 months in the placebo treated group ([Garcia-Manero, 2008a](#)), which takes into account possible cross-over outside of the protocol of placebo treated

subjects to active treatment during the observation period, and a median OS of 25.7 months (43% improvement) in the oral azacitidine treated group, 216 subjects (108 in each group) would have approximately 72% power to detect a constant hazard rate ratio of 0.70 using a two-sided log rank test with overall significance level of 0.05. It is assumed that the OS distribution is exponential with a constant failure (hazard) rate and that accrual is uniform during the accrual period (56 months) with an overall drop-out rate of 5% from both treatment groups. Full information necessary for a log rank test to have 72% power will be achieved when approximately 205 deaths have occurred in both treatment groups, which is expected approximately 134 months after randomization of the first subject into the study.

An interim analysis of the OS endpoint will be performed and reported when all subjects have completed 12 months [52 weeks (364 days)] of double-blind treatment or have been discontinued from treatment (see Section 15).

While 56 days (8 weeks) is the standard response criteria for hematologic improvement (IWG 2006 criteria; Cheson, 2006; Appendix E), limited information is available on the target population for estimating the response rate for the primary endpoint of RBC transfusion independence maintained for ≥ 84 days (12 weeks).

A total sample size of 216 subjects (108 in the active treatment group and 108 in the placebo group) will have approximately 99% power to detect the difference between a response rate of 0.30 in the active treatment group and a response rate of 0.05 in the placebo group, and approximately 70% power to detect the difference between a response rate of 0.15 in the active treatment group and a response rate of 0.05 in the placebo group. The power calculations for response rate are based on a two-sided alpha of 0.05 and test statistics on the difference of proportions using an un-pooled estimate of variance.

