10.1. Analysis of Primary Efficacy Endpoint

The primary efficacy endpoint of RBC transfusion independence is defined as the absence of any RBC transfusion during any consecutive "rolling" 56 days within the treatment period. A subject who did not receive any RBC transfusion during a consecutive rolling 56 days (i.e., day 1 to day 56, day 2 to day 57) will be considered as a 56-day RBC transfusion independent responder. Subjects without achieving the response as defined above, subjects with less than 56 days of assessment during the double-blind treatment period, and subjects who had average baseline RBC transfusion units less than 2 units per 28 days (as defined in Section 8.2) will be counted as non-responders.

All RBC transfusion records on or after randomization within the evaluation period will be used to assess the response for each subject. In other words, the days after the end of the evaluation period will not contribute to a rolling period. The end date of the evaluation period is defined as:

- For a subject who discontinues the treatment,

- If the subject doesn't receive a subsequent MDS treatment, use the date of end of treatment visit;
- If the subject receives a subsequent MDS treatment, use the start date of the subsequent MDS treatment – 1 day, or the date of end of treatment visit, whichever is earlier;
- For a subject who is still on-treatment at the time of the database lock for the primary analysis, the subject's latest available assessment date in the database (from AE, vital sign, local and central lab, study drug records, efficacy assessments) will be used.

The 56-day rolling period for the RBS transfusion independent assessment starts on the date of randomization.

Note if the interval between the last RBC transfusion in the evaluation period (if there is at least one RBC transfusion during the evaluation period) and the end date of the evaluation period is less than 56 days, this rolling period, which is less than 56 days, won't be considered as meeting the transfusion independence criteria even though there is no RBC transfusion in it. The day on which the transfusion is received will not contribute to the 56-day without receiving RBC transfusion rolling period.

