10.2.1. Key Secondary Endpoint

Overall survival (OS), defined as the time from randomization to death from any cause, will be calculated using randomization date and date of death, or date of last follow-up for censored subjects. Time to death is defined as the time between randomization and death from any cause. All subjects will be followed until drop-out, death, or study closure. Drop-out may be due to withdrawal of consent from further data collection or lost to follow-up. Subjects who drop-out or are alive at study closure (or at the time of the interim analysis [Section 15.2]) will have their OS times censored at the date of last known alive, as appropriate.

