10.2.5. Time to RBC transfusion independence of ≥ 56 days (8 weeks)

Time to RBC transfusion independence of ≥ 56 days is defined as the time between randomization and the date onset of transfusion independence is first observed (ie, Day 1 of 56 without any RBC transfusions). Subjects who do not achieve RBC transfusion independence

during the treatment period will be censored at the end date of evaluation period which is defined in Section 10.1. In case a subject has more than one rolling periods which meet the independence criteria, the time to the first rolling period will be used in the analysis. Time to RBC transfusion independence curves will be estimated using KM methods and treatment groups will be compared using a stratified log-rank test. A stratified Cox proportional hazards model will be used to estimate the corresponding hazard ratio and 95% CI. Time to RBC transfusion independence (in month) for at least 56 days will also be summarized using descriptive statistics based on subjects who achieve the response.

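### SAP 10.3 splits overall survival from randomization by a response reached later, so guaranteed survival time favours responders; the pooled version also mixes response with arm

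*SAP*

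**What the plan says.** The last paragraph of SAP 10.3 plans: "The OS will also be explored by whether a subject achieves RBC transfusion independence for at least 56 days or not". Kaplan-Meier medians and quartiles with 95% CIs are "summarized for each subgroup group (Responders and Non-responders), unadjusted for the stratification variables". On populations: "This will be explored for all subjects in ITT population as well as for subjects within oral azacitidine arm and within Placebo arm".

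Two definitions feed this summary.

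- SAP 10.2.1 sets the time origin: "Overall survival (OS), defined as the time from randomization to death from any cause".
- SAP 10.1 requires 56 consecutive transfusion-free days inside an evaluation period. That period ends at the end-of-treatment visit, or the day before subsequent MDS therapy if that is earlier. Non-responders include "Subjects without achieving the response as defined above, subjects with less than 56 days of assessment during the double-blind treatment period".

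The SAP gives no landmark, time-dependent covariate or caveat for this comparison. It also plans no test or hazard ratio for it. Protocol 10.6.2.3 does not list the analysis.

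**The concern.** The groups are formed by an event after randomization, but survival is counted from randomization. A responder cannot die before the qualifying 56 days end, so that stretch is guaranteed survival time. Any death before Day 56 is a non-responder death by definition. The responder curve is then higher in expectation even when response has no bearing on survival.

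Two statements in the protocol make this more than a technicality here. Section 4.2 expects response to azacitidine to be delayed, which lengthens the guaranteed time. Section 1.4.1 reports that most deaths on oral azacitidine came in the first 56 days of treatment, mainly from infection. This table could present early deaths on active drug as poor survival of non-responders.

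The pooled version has a second problem. The plan assumes that arm affects both response and survival, so responders would come mostly from one arm. At stake is a set of medians and CIs that a reader would naturally take as evidence that transfusion independence prolongs life.

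**Working it through.** **Inputs (SAP 4.4).** Exponential survival with medians of 18 months (placebo) and 25.7 months (azacitidine), 108 subjects per arm, and "a response rate of 0.30 in the active treatment group and a response rate of 0.05 in the placebo group". The SAP converts days to months by dividing by 30.4375.

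**The plan's own figures reproduce.** The hazard ratio is 18/25.7 = 0.700. Log-rank power with 205 deaths: √(205/4) × |ln 0.70| − 1.96 = 2.553 − 1.96 = 0.593, or 72.4% (stated 72%). Response power with unpooled variance is 99.9% for 0.30 versus 0.05 (stated approximately 99%) and 70.0% for 0.15 versus 0.05 (stated 70%).

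**Smallest bias, by hand.** Let response have no effect on survival and let every response start at day 0. The guaranteed time is w = 56/30.4375 = 1.84 months.

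- Deaths before Day 56: 1 − 2^(−1.84/25.7) = 4.8% on azacitidine; 1 − 2^(−1.84/18) = 6.8% on placebo.
- Responder median, by lack of memory: 25.7 + 1.84 = 27.5; 18 + 1.84 = 19.8.
- Non-responder survival beyond w, with observed response share p: S(t) × [1 − p/S(w)]/(1 − p). For p = 0.30 and median 25.7, S(w) = 0.952 and the factor is 0.978. The median solves S(t) = 0.5/0.978 = 0.511, giving 24.9 months.

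**Later onset, by simulation.** The documents give no onset distribution for this endpoint, so it was assumed and ranged: day 0, uniform over 0–6 months, or uniform over 0–12 months. Treatment stops were absent, or exponential with a median of 9 or 6 months. Response counted only if onset plus 56 days preceded death and treatment stop. Observed response was fixed at 30%, with 1,000,000 subjects per scenario and no true effect.

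| True median (months) | Onset | Responder median | Non-responder median |
|---|---|---|---|
| 25.7 | day 0 | 27.5 | 24.9 |
| 25.7 | 0–6 months | about 30 | about 23.5 |
| 25.7 | 0–12 months | about 32–33 | about 22 |
| 18 | day 0 | about 20 | about 17 |
| 18 | 0–6 months | about 22.5 | about 15.7 |
| 18 | 0–12 months | about 24–25.5 | about 14–14.7 |

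The gap runs from 2.5 to 11.6 months. At the planned placebo rate of 5% and a median of 18, it is about 1.9 to 8.1 months. In single arms of 108 with 30% responders and follow-up of 12 to 68 months (56 months' accrual plus 12), the responder median was the higher one in about 63% to 94% of null trials at a median of 25.7, and 69% to 99% at 18. Without bias it would be about 50%.

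**Extra early deaths.** Adding an assumed 5% or 10% of azacitidine deaths in the first 56 days (latent response 30%, exponential onset with mean 84 days) gave null medians of 30.2 versus 21.3 and 30.2 versus 18.7 months.

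**Confounding by arm alone.** At the planned rates azacitidine supplies 0.30/0.35 = 86% of responders and 0.70/1.65 = 42% of non-responders. With no guaranteed time at all, the pooled death-rate ratio is (0.424 × 25.7 + 0.576 × 18)/(0.857 × 25.7 + 0.143 × 18) = 21.27/24.60 = 0.86. With both problems, the pooled medians run from 26.2 versus 20.4 to 32.0 versus 19.1 months.

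**Remedies under the same null.**

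- Day-168 landmark: within-arm medians agree to within 0.2 months. The pooled rate ratio stays near 0.87 unstratified and becomes 1.00 when stratified by arm.
- Time-dependent response switched on at the end of the 56 days: rate ratio 1.00.
- The same model switched on at the SAP 10.2.5 onset, "the date onset of transfusion independence is first observed (ie, Day 1 of 56 without any RBC transfusions": 0.87 to 0.90 with follow-up of 12 to 68 months, because 56 guaranteed days remain.

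**The case against.** The mechanism is hard to dispute; the case on the other side is about weight and calibration.

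- **Scope.** This is one exploratory paragraph with no test, hazard ratio or alpha. A caveat would remove much of the harm. That stands, and it limits the severity.
- **The upper end.** Gaps above about 11 months need onset spread evenly over a year and no treatment stops. With stops, the 0–12-month gap falls to about 9.5 to 10.2 months. Protocol 1.2 cites a retrospective lower-risk series in which 77% of responses came within six cycles. That was overall response, not oral-drug transfusion independence, but it makes the 0–6-month rows (gaps of roughly 6.4 to 7.1 months) the better central guide.
- **Inputs.** An 18-month median with 30% responders is not a planned combination. It describes an azacitidine arm with no survival benefit.
- **Recoverability.** SAP 10.1 and 10.2.5 plan subject listings and onset summaries, so someone holding those data could redo the analysis. A reader of the medians alone could not.
- **Arm confounding.** It is conditional. With equal survival in both arms it vanishes, although guaranteed time remains (pooled 22.5 versus 17.1 months at a common median of 18). An azacitidine survival deficit would reverse its direction. This argues for stratifying by arm or dropping the pooled version.
- **Timing.** The SAP was signed in March 2019 and the primary study report was final by 04-Feb-2020, so a landmark chosen now is post hoc. However, SAP Section 2 leaves the final survival analysis for later.

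**Conclusion.** The concern holds. As written, the summary favours responders in expectation, within each arm and pooled, for a reason unrelated to response. The floor, with onset at day 0, is about 2.5 to 2.7 months between medians at 30% responders. Plausible delayed onset raises it to roughly 6 to 7 months, and the extreme assumption to 11.6. These sizes rest on exponential survival, on response being independent of survival within arm, and on assumed onset and treatment-stop times. The direction of the guaranteed-time bias does not depend on those times. The arm confounding favours responders under the planning assumptions and follows the sign of any true survival difference between arms. The primary endpoint, the confirmatory survival test and the alpha control in SAP 10 and 10.2 are unaffected. The analysis should be corrected, but it does not threaten the trial's main conclusions.

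**What to change.** Replace the last paragraph of SAP 10.3 with a within-arm landmark analysis:

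- Fix the landmark at Day 168 from randomization. Do not tie it to the end of Cycle 6, since "Day 1 of Cycles 2 and beyond may be delayed from Day 28 of the prior cycle".
- Include subjects alive and in follow-up at Day 168.
- Classify them by whether a full 56-day transfusion-free period was completed by then.
- Measure survival from Day 168.

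Instead, or in addition so that later responses are credited, fit a Cox model with response as a time-dependent covariate. Switch it on at the end of the 56 days, not at the SAP 10.2.5 onset date. Stratify any pooled version by arm, or drop it. Omit the placebo version if responders are too few; 108 × 0.05 gives about 5. Label all output as a non-causal comparison on a post-randomization event, state that the landmark was chosen after unblinding, and attach the same caveat to any version already reported.

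The cost is a few lines of SAP text and one altered program. The landmark drops deaths before Day 168 and counts responses completed later as non-response. Among responders alive at Day 168 it credits all of them if onset is at day 0, about 62% to 70% if onset is spread over 0–6 months, and about 33% to 50% over 0–12 months. The time-dependent model avoids that loss, but introduces a hazard ratio where none is now planned.
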